11.3 Determination of Sample Size

The primary objectives of phase 1 of the study are to evaluate the safety of Sl-401 as a single agent in an initial Run-in Cycle, to determine the MTD or the maximum tested dose where multiple DLTs are not observed and to further characterize the safety profile of SL-401/POM//DEX at the MTD. Based on such a recommended dose for phase 2 studies will be defined. A maximum of 3 dose levels (7, 9, and 12 μg/kg/day) is anticipated and thus the total number of patient for this stage ranges from 6 to 18. The anticipated same size is sufficient to evaluate these objectives. A secondary objective is to characterize the anti-tumor activity of SL-401/POM/DEX in terms of ORR, CBR, PFS and PFS-6. During phase 2, if approximately 14 patients are enrolled at the recommended phase 2 dose as defined in phase 1 over 12 months and follow-up continues for 12 months after the last enrolled patient, the total of 20 patients treated at this dose has approximately 75% power with a 1-sided type I error rate of 5% to reject the null hypothesis that the PFS-6 is <40% if the true rate is 60%.

11.4 Demographics and Baseline Characteristics

Demographic (e.g., gender, age, race) and baseline characteristics (e.g., ECOG performance status, height, weight, and prior therapy) will be summarized by SL-401 dose group with descriptive statistics.

11.5 Analyses of Safety Data

Safety assessments include DLTs, AEs, SAEs, physical examinations, vital sign measurements, ECGs, clinical laboratory evaluations, and reasons for treatment discontinuation due to toxicity. The AE reporting period for a patient treated in the study begins with the initiation of SL-401 or SL-401/POM/DEX and is continuous through 30 days after the last dose of SL-401 or SL-401/POM/DEX. All AEs that occur in treated patients during the AE reporting period specified in the protocol must be reported to the Sponsor, whether or not the event is considered related to SL-401/POM/DEX. Any known untoward event that occurs beyond the AE reporting period that the Investigator assesses as related to SL-401/POM/DEX should also be reported as an AE.

Treatment-emergent adverse events through 30 days after last dose of SL-401/POM/DEX will be summarized by MedDRA™ Version 13.1 (or higher) System Organ Class and preferred term. The incidences and percentages of patients experiencing each AE preferred term will be summarized with descriptive statistics. AEs will also be summarized by NCI CTCAE, v.4.03 (or higher), grade and by causality (relationship to study drug). Dose-limiting toxicities, grade 3-4 AEs, SAEs, and AEs resulting in dose modification or treatment discontinuation will also be summarized by preferred term.

Laboratory results will be classified according to NCI CTCAE, v.4.03. Laboratory results not corresponding to an NCI CTCAE term will not be graded. Incidences of laboratory abnormalities will be summarized with descriptive statistics.

Vital signs, physical examination results, and ECGs will be summarized with descriptive statistics.

11.6 Analyses of Efficacy Data

The study will preliminary evaluate the activity of the SL-410/POM/DEX regimen. Secondary efficacy endpoints will include: PFS and PFS-6; ORR (CR + VGPR + PR) and clinical benefit rate (CR + VGPR + PR + MR) based on IMWG defined response criteria, as well as DOR; and OS. Response rates and depth of response will be calculated as the percent of evaluable patients that have confirmed sCR/CR/VGPR or PR, and exact 95% confidence intervals will be calculated for these estimates. Time to response, duration of response, and survival will be estimated using the product-limit method of Kaplan and Meier. For subgroups of patients defined by disease and line of therapy, exact 1-sided 95% confidence intervals will be calculated

for ORR and clinical benefit rates, and the distributions for duration of response, PFS, PFS6, and OS will be estimated by Kaplan-Meier methodology.

Efficacy assessment parameters will include:

- M-protein determination using both of the following procedures:
 - SPEP and serum protein immunofixation with quantitative immunoglobulins; and
 - UPEP and urine protein immunofixation (all using the same 24-hour urine collection)
- Serum FLC
- BM to quantify percent MM cell involvement
- Plasmacytoma evaluation: PET/CT scan or MRI and or physical exam as clinically indicated
- Skeletal survey
- Serum β2 microglobulin
- Cytogenetic analysis/FISH from BM aspirate

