3.5.5 Pomalidomide

Pomalidomide (POM), an analog of thalidomide, is an Immunomodulatory Drug (IMiD) with antineoplastic activity. In *in vitro* cellular assays, POM inhibits proliferation and induces apoptosis of hematopoietic tumor cells. Additionally, POM has been demonstrated to inhibit the proliferation of lenalidomide-resistant MM cell lines and synergizes with dexamethasone (DEX) in both lenalidomide-sensitive and lenalidomide-resistant cell lines to induce tumor cell apoptosis. POM has also been shown to enhance T cell- and natural killer cell-mediated immunity and inhibit production of pro-inflammatory cytokines (e.g., tumor necrosis factor-α and IL-6) by monocytes.

POM is indicated for patients with MM who have received at least 2 prior therapies including lenalidomide and bortezomib and have demonstrated disease progression on or within 60 days of completion of the last therapy.

A phase 2 study randomized 221 patients to received either POM and DEX (n = 113) or POM alone (n = 108) (Richardson 2014). The efficacy of POM was enhanced by the addition of DEX; with a median follow-up of 14.2 months, median progression-free survival (PFS) was 4.2 and 2.7 months and the overall response rate (ORR) was 33% and 18% (P = 0.013) respectively. In a subsequent Phase 3 study of patients with advanced MM who had exhausted bortezomib and lenalidomide treatment the benefits of POM and low-dose DEX were further demonstrated in terms of PFS (4.0 months) and OS (12.7 months) versus high-dose DEX, the standard of supportive care (PFS 1.9 months and OS 8.1 months) (San Miguel 2013). POM and low-dose DEX are generally well tolerated, and provide an important new treatment option for relapsed/refractory multiple myeloma (RRMM) patients who have received multiple prior therapies. However, all patients ultimately progress with no further treatment options or die from their disease. Further studies are warranted to evaluate the use of POM in combination with other novel agents to improve upon these outcomes.

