9.7 Follow-Up

Patients who discontinue therapy for reasons other than MM progression will be followed for disease response every month until progression of disease or initiation of subsequent therapy. Patients who have discontinued study therapy and have had MM progression should be contacted approximately every 3 months (telephone contact is permitted) to assess survival status for up to one year; patients who discontinue therapy for reasons other than disease progression and are no longer willing to follow-up for evaluation of disease progression should also be contacted for survival status whenever feasible.

Table 13: Schedule of Events

	Screening/ Baseline	Run in Cycle Cycle is 28 days																	
Evaluation	D-21 to -1	D 1	D 2	D 3	D 4	D 5	D 8	D 15	D 22	D 1	D 2	D 3	D 4	D 5	D 8	D 15	D 22	EOT	F/Uw
Informed Consent & Pomalyst REMS ^a	х																		
Entry Criteria Review	Х											,							
Medical and Myeloma History	x																		
Physical Examination ^c	X	X	Х	Х	Х	Х	X	Х	Х	х	X	Х	Х	Х	Х	X	Х	X	
Performance Status (ECOG)	х	x								х								x	
Height (Baseline only) / Weight	х	x	х	х	х	х	x	х	х	х	х	х	х	х	х	х	х	х	
Vital Signs (HR, Temperature, RR, $\mathrm{BP})^{\mathrm{d}}$	x	X	x	х	х	х	x	x		х	х	x	x	x	x	x		x	
ECG	X									х								х	
ECHO/MUGA	х								77										
Pregnancy testing [FCBP) and counseling *	х								Xe	х					Xe	Xe	Xe	х	
Hematology	X	x	x	х	х	х	x	x	x	Xf	x	х	х	x	х	x	х	x	
Serum Chemistry®	X	X	X	Х	х	X	X	X	X	Х	х	Х	X	Х	X	X	Х	X	
PT / INR aPTT	х									х								x	
Urinalysis h	Х	X								х								х	
Plasmacytoma Evaluation ⁱ	x									Xi								x	As needed
Skeletal Survey j	X																		As needed
Bone Marrow Aspiration and biopsy ^k	х									Xk								х	
Peripheral blood for correlative studies ¹	x									Xl								x	

	Screening/ Baseline				Run ir ycle is					Cycles 1 - 6 ⁿ Each Cycle is 28 days									
Evaluation	D-21 to -1	D 1	D 2	D 3	D 4	D 5	D 8	D 15	D 22	D 1	D 2	D 3	D 4	D 5	D 8	D 15	D 22	ЕОТ	F/U ^w
Myeloma-specific Laboratory Tests ^m	x	х								х								х	As needed
PK (SL-401) ⁿ		Х				х				X C2				X C2				x	
Immunogenicity (SL-401)°		x				х				х								x	
SL-401 Pre-medication ^p		x	x	x	x	x				x	x	x	x	x					
SL-401 Administration ^q		х	X	Х	Х	Х				Х	X	х	х	Х					
Pomalidomide ^r										Days 1 - 21									
Dexamethasone										x					x	x	x		
Adverse Event monitoring ⁶	x		← X →							x									
Prior/Concomitant Medication ^t	x			← X →							x								

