- k. Bone Marrow Aspiration: Bone marrow aspiration for cytogenetic analysis both by FISH and standard karyotyping, and morphologic evaluation including assessment of plasma cell percentage is required at screening/baseline (within 21 days prior to study drug administration. Bone marrow aspirate should be repeated if CR or stringent complete response (sCR) is suspected to confirm achievement of response according to IMWG criteria, and at End of therapy. Additional BM aspirate material (10-15cc if feasible) and biopsy for correlative studies are to be collected at baseline and any time a specimen is obtained to confirm response.
- Peripheral blood for correlative studies should be obtained at baseline, for phase 1 Day 1 of Cycles 1, 3, and 5 and for phase 2 on Day 1 of Cycles 2, 4, and 6 and at EOT for all patients. Four 10 mL tubes in total (3 green top, 1 red top/serum separator tube). Whole blood will be evaluated for circulating MM/plasma cells (and other mononuclear cells of interest); serum and plasma will be for evaluated for potentially relevant circulating cytokines, and surrogate markers of osteolytic activity.
- m. Myeloma-specific laboratory tests: β2 Microglobulin (at baseline only), serum and 24-hour urine immunoelectrophoresis, serum immunoglobulin assay, serum/urine immunofixation and serum FLC with kappa/lambda ratio to be performed at baseline, every cycle prior to study drug administration thereafter and at end of treatment (if last tests were > 4 weeks) and for patients who discontinue therapy for reasons other than disease progression. Myeloma laboratory tests will be repeated every month until disease progression or initiation of subsequent therapy. Response assessment will be done at the beginning of every cycle. Following pre-treatment evaluations on Day 1 of the first cycle evaluations may be performed on Day 1 of a subsequent cycle or during the 7 days prior to Day 1 of the Cycle as needed for scheduling. (Note that an evaluation performed during the final week of Cycle 1 should nonetheless be recorded as the evaluation for the beginning of Cycle 2, with similar assignments for subsequent cycles).

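### Kaplan-Meier for time to response, if patients who progress or die first are censored, overstates the cumulative proportion responding; cumulative incidence should replace it (minor)

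*Protocol*

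**What the plan says.** Section 11.6 of the protocol names the estimator: "Time to response, duration of response, and survival will be estimated using the product-limit method of Kaplan and Meier". It gives no population for time to response and no rule for patients who progress or die before responding.

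The sentence before it handles the proportion responding separately: "Response rates and depth of response will be calculated as the percent of evaluable patients that have confirmed sCR/CR/VGPR or PR", with exact 95% confidence intervals.

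On follow-up, section 9.7 says that patients who stop therapy for reasons other than progression "will be followed for disease response every month until progression of disease or initiation of subsequent therapy". Note m to Table 13 adds: "Response assessment will be done at the beginning of every cycle". After progression, sections 6.4, 7.9.2 and 9.7 provide for survival contact only.

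For background, section 3.5.5 reports on the randomised phase 2 comparison of pomalidomide with and without dexamethasone: "median progression-free survival (PFS) was 4.2 and 2.7 months and the overall response rate (ORR) was 33% and 18" percent. The first figure of each pair is the combination.

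**The concern.** A patient who progresses, dies or starts another anti-myeloma treatment can no longer respond to the study regimen. Kaplan-Meier treats a censored patient as still able to respond later, at the same rate as those still under observation. If non-responders are censored at progression, the curve redistributes their probability to later responses that cannot occur.

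On the background figures about two thirds of patients never respond, so the competing event is more common than the event being estimated. A report could then show a response rate of 33% beside a curve that climbs well above it, together with a median time to response that does not exist in the treated population.

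**Working it through.** **Plan's own figure.** The protocol gives no figure for time to response, so there is none to reproduce. Its only design calculation is the power for PFS-6 in section 11.3, which does not involve this curve. Two of its inputs serve below: PFS-6 of 40% and 60% correspond, under exponential PFS, to medians of 6·ln2/(−ln 0.4) = 4.54 and 6·ln2/(−ln 0.6) = 8.14 months.

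**Inputs.** Response rate 33% and median PFS 4.2 months come from section 3.5.5. Assumed, because the protocol does not give them: constant hazards, the PFS hazard applying to patients who have not yet responded, and, for sensitivity, response rates of 45% and 60%.

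**Formulas.** With response hazard r and competing hazard c:
- cumulative incidence: CIF(t) = r/(r+c) × [1 − exp(−(r+c)t)]
- complement of Kaplan-Meier with competing events censored: 1 − KM(t) = 1 − exp(−rt)

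**Case 1: 33% respond eventually.** c = ln2/4.2 = 0.165 per month, and r/(r+c) = 0.33 gives r = 0.081.
- At 6 months, CIF = 0.33 × (1 − exp(−0.246×6)) = 25.5% and 1 − KM = 1 − exp(−0.0813×6) = 38.6%. The excess is 13.1 points. The standard error of the CIF with 20 patients is √(0.255×0.745/20) = 9.7 points.
- 1 − KM crosses 50% at ln2/0.0813 = 8.5 months, although the CIF never exceeds 33%.

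**Case 2: 33% have responded by 6 months.** Solving CIF(6) = 0.33 with the same c gives r = 0.113 and 1 − KM(6) = 49.3%. The excess is 16.3 points.

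**Sensitivity to timing.** Responses are now assigned by 28-day cycle (0.92 months) over six cycles. In each cycle, KM is multiplied by 1 − (new responders / at risk), responders are removed, and a fraction 1 − exp(−0.92c) of the remainder is removed as competing events. Excess of 1 − KM over CIF, in points:

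| Response timing | Response rate | Median PFS 4.2 months | Median PFS 8.14 months |
|---|---|---|---|
| Early (60/30/10% in cycles 1–3) | 33% | 2.8 | 1.4 |
| | 60% | 5.1 | 2.5 |
| Intermediate (40/25/15/10/5/5%) | 33% | 8.3 | 3.8 |
| | 60% | 15.0 | 6.9 |
| Even over six cycles | 33% | 16.9 | 7.5 |
| | 60% | 30.7 | 13.6 |
| Constant hazards, as in case 2 | 33% | 16.3 | 8.2 |
| | 60% | 22.9 | 12.7 |

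Results for a 45% response rate lie between those for 33% and 60%.

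**Worked example, 20 patients with 7 responders (35%).**
- Early: responses 4, 2, 1 in cycles 1–3, competing events 1, 2 in cycles 1–2. 1 − (16/20)(13/15)(10/11) = 37.0%.
- Spread out: responses 2, 1, 1, 1, 1, 1, competing events 1, 2, 2, 2, 2 in cycles 1–5. 1 − (18/20)(16/17)(13/14)(10/11)(7/8)(4/5) = 49.9%.
- Non-responders held in the risk set to the end: 35.0%, with no excess.

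**The case against.** The strongest reply is that section 11.6 names an estimator and nothing more. It does not say that non-responders are censored at progression. Analysing responders only, or keeping non-responders at risk to the end of follow-up, also uses the product-limit method and gives no excess. Duration of response stands in the same sentence, also without a population, and can only concern responders. Population and censoring rules commonly belong in the SAP, which is not at hand.

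Part of this stands: the censoring rule is an inference. It is the natural one, however. Among responders every response time is observed, so nothing is censored and the product-limit method reduces to the plain empirical distribution. Naming it suggests that non-responders are included, and response follow-up stops at progression or new therapy. The point also concerns an estimator that the protocol itself prescribes, not a detail it leaves open.

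Two stronger readings are tempting, and the documents do not support them. A reader might infer a general excess of at least 10 points. The protocol gives no response timing, and even at 33% response and a median PFS of 4.2 months the excess is only 2.8 points with early responses and 8.3 with intermediate timing. Extending case 1 to 12 months gives 62.3% against 31.3%, but only exp(−0.246×12) = 5% of patients, about 1 in 20, would then be at risk. A reader might also infer that the reported response rate is inflated. It is not: it is a simple percentage of evaluable patients with an exact interval.

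**Conclusion.** The point holds in conditional form. If patients who progress, die or start new therapy without responding are censored, the direction is certain: one minus Kaplan-Meier exceeds the cumulative proportion responding. The size rests on assumptions outside the protocol: about 13 to 16 points at 6 months with its background figures and constant hazards, about 1 to 31 points over the timings, response rates and progression rates tried, and zero for a responders-only analysis.

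Severity is minor. Time to response is not an objective and not among the listed secondary endpoints, and the synopsis omits it from the Kaplan-Meier analyses. No hypothesis, sample size or dose decision uses it. What is at risk is a misleading descriptive curve and median, not a trial conclusion.

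**What to change.** In section 11.6, take time to response out of the Kaplan-Meier sentence. State that it will be estimated in all treated patients (or all evaluable patients, with the choice named) by the cumulative incidence function (Aalen-Johansen), with progression, death or new anti-myeloma therapy before response as competing events. Give the median and range of time to response among responders as a descriptive companion. Keep Kaplan-Meier for PFS, OS and duration of response.

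If only responders were intended, the sentence should say so.

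The cost is one sentence and standard software, with no change to data collection or sample size. The reported curve will be lower and may have no median. Without other loss to follow-up, it will end at the observed proportion responding in the population chosen.

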11.7 Translational, Pharmacokinetic, and Immunogenicity Analyses

Planned translational, PK, and immunogenicity analyses will be described in separate analysis plans.

11.8 Blinding

This is an open-label study.

12 Emergency Procedures

12.1 Emergency Contact

In emergencies, the Investigator should contact the Medical Monitor by telephone at the number listed on the title page of the protocol.

12.2 Emergency Treatment

During a patient's participation in the study, the Investigator and/or institution should ensure that adequate medical care is provided to a patient for any AEs, including clinically significant laboratory values, related to the study.

13 Ethical and Regulatory Considerations

13.1 Good Clinical Practice

As the Sponsor of this clinical study, Stemline Therapeutics Inc. has the overall responsibility for the conduct of the study, including assurance that the study meets the requirements of applicable regulatory authorities. Stemline will maintain compliance with the FDA Code of Federal Regulations, International Conference of Harmonisation (ICH) Guideline E6, Declaration of Helsinki, and Good Clinical Practice (GCP) Guidelines. The study must receive approval from an Institutional Review Board (IRB) or Independent Ethics Committee (IEC) prior to commencement. The Investigator will conduct all aspects of this study in accordance with applicable national, state, and local laws of the pertinent regulatory authorities.

The Sponsor is responsible for obtaining IRB approvals, providing Investigators with information required to conduct the study, ensuring proper investigative site monitoring, verifying that appropriate patient informed consent is obtained, submitting an IND to FDA, and ensuring that the IRB and regulatory agencies are promptly informed of significant new information regarding the study.

13.2 Delegation of Investigator Responsibilities

The Investigator must ensure that all persons assisting with the study are adequately informed about the protocol, any amendments to the protocol, the study drugs, and their study-related duties and functions. The Investigator should maintain a list of sub-investigators and other appropriately qualified persons to whom he or she has delegated significant study-related duties.

13.3 Patient Information and Informed Consent

Before being admitted to the clinical study, the patient must consent to participate after the nature, scope, and possible consequences of the clinical study have been explained in a language understandable to him or her. An Informed Consent Form (ICF) that includes both information about the study and the consent form will be prepared and given to the patient. This document will contain all ICH, GCP, and locally required regulatory elements. The ICF must specify who informed the patient and be approved by the Institution's IRB. Copies of the ICF used in the study must contain the IRB-approval stamp (if applicable) and version date. The Investigator must keep the original executed ICF including the patients' signatures and the signing dates properly stored in a secured location at the study site with an additional copy of the ICF attached to the patients' eCRFs and therapy records.

After reading the ICF, the patient must give consent in writing. The written informed consent will be obtained prior to conducting any study-related procedures or tests. The patient's consent must be confirmed at the time of consent by the dated signature of the person conducting the informed consent discussions. If the patient agrees to participate in the study, the patient and the Investigator must sign both copies of the ICF. A copy of the signed ICF must be given to the

patient or the patient's legally authorized representative. The signed ICF must be available for verification by the Sponsor's designated monitors or FDA inspectors.

The date of the signed ICF will also be noted in the patient's medical chart. Patients should be informed of new information learned during the study, which may affect their decision to continue participation in the study. The Investigator should inform the patient's primary physician about the patient's participation in the study if the patient has a primary physician and if the patient agrees to the primary physician being informed.

13.4 Confidentiality

The Investigator(s) and the Sponsor or its authorized representative will preserve the confidentiality of all patients and donors participating in the study, in accordance with GCP, local regulations and to the extent applicable the Health Insurance Portability and Accountability Act of 1996 ("HIPAA").

Patient names will not be supplied to the Sponsor or its authorized representative. Only the patient study numbers and (if permitted by the institution) patient initials will be recorded in the eCRF, and if the patient name appears on any other document (e.g., pathologist report), it must be obliterated before a copy of the document is supplied to the Sponsor or its authorized representative. Study findings stored on a computer will be stored in accordance with local data protection laws. Patients will be told that representatives of the Sponsor, its authorized representative, IRB or IEC, or regulatory authorities may inspect their medical records to verify the information collected, and that all personal information made available for inspection will be handled in strictest confidence and in accordance with local data protection law. The Investigator will maintain a personal patient identification list (patient numbers with the corresponding patient names) to enable records to be identified.

